
Study plan
	
After verification of any inclusion/exclusion criteria the patients will be included in the study and randomised to the poractant alfa group or to standard of care one.
 
Poractant alfa group
 
 - Starting from patient intubation and mechanical ventilation, defined assessments will be collected (for details see study schedule 7.1). - Patients will receive three poractant alfa endotracheal administrations 24 hours apart. - Defined assessments will be collected before randomisation and at 6 -12 - 24 hours after each poractant alfa administration till 72 hours since the first administration. - From Day 4 to Day 27 assessment collection will occur every 24 hours until Intensive Care Unit (ICU) discharge. Whenever the discharge occurs, additional safety lab and SOFA assessments will be collected. - At Day 28 the last follow up evaluation will occur on the ICU if still requiring critical care, or by phone call if the patient has been discharged from ICU by that time. 
Control group
 
 - Starting from patient intubation and mechanical ventilation defined assessments will be collected (for details see study schedule 7.1). - Defined assessments will be collected before randomisation and at specific timepoints (according to study schedule 7.1) from

Clinical Study Code No.: CLI-050000-04	Version No.: 4.0
EUDRACT No.: 2020-002632-75 – IND No: 153286	Date: 02 MAR 2021

	
randomisation up to 72 hours.
 
 - From Day 4 to Day 27 assessment data collection (according to study schedule 7.1) will occur every 24 hours until Intensive Care Unit (ICU) discharge. Whenever discharge occurs, assessment data will be collected at the corresponding Day X. - At Day 28 the last follow up evaluation will occur on the ICU, or by phone call if the patient has already been discharged.

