Poractant alfa treated group	ICU stay period					ICU discharge	Last FUP
	Screening ⁷	Day 1 (Randomisation)	Day 2	Day 3	Day 4 – 27	Day X	Day 28
		Before randomisation/treatment and 6-12-24h after each administration up to 72 hours			Every 24h till ICU discharge	Whenever it occurs	
Control group	Screening	Time 72 h			Day 4 – 27	Day X	Day 28
		Before randomisation and at 6, 12, 24, 30, 36, 48, 54, 60, 72 h since randomisation			Every 24h till ICU discharge	Whenever it occurs	
Mechanics Laboratory assessments ³		Treated group: Before randomisation and 12, 24, 48, 72, after first administration Control group: Before randomisation and 12, 24, 48, 72, after randomisation			Treated group: 96h after first administration Control group: 96h after randomisation		
Laboratory assessments ⁴	X			Once Treated group: 24h post last treatment Control group: 72h post randomisation		X	Once if not discharged from ICU
SOFA score ⁵	X			Once Treated group: 24h post last treatment Control group: 72h post randomisation		X	Once if not discharged from ICU
Thoracic CT scan or Chest XR ⁶	X						
Curosurf administration (intreated group)		Three ET administrations with a 24 hours interval (Day 1, Day 2 and Day 3)					
Concomitant Medications	X	X	X	X	X	X	X

Clinical Study Code No.: CLI-050000-04	Version No.: 4.0
EUDRACT No.: 2020-002632-75 – IND No: 153286	Date: 02 MAR 2021

Poractant alfa treated group	ICU stay period					ICU discharge	Last FUP
	Screening ⁷	Day 1 (Randomisation)	Day 2	Day 3	Day 4 – 27	Day X	Day 28
		Before randomisation/treatment and 6-12-24h after each administration up to 72 hours			Every 24h till ICU discharge	Whenever it occurs	
Control group	Screening	Time 72 h			Day 4 – 27	Day X	Day 28
		Before randomisation and at 6, 12, 24, 30, 36, 48, 54, 60, 72 h since randomisation			Every 24h till ICU discharge	Whenever it occurs	
Adverse Events	X	X	X	X	X	X	X
Ventilatory support	X	X	X	X	X	X	X
Concomitant procedures	X	X	X	X	X	X	X

- ¹ Arterial blood gas (ABG) analysis: pH, pCO₂, pO₂, HCO₃, lactate.
- ² Ventilatory parameters: PaO₂/FiO₂, FiO₂, TV (tidal volume), RR (respiratory rate), Cstat (static compliance), Cdyn (dynamic compliance), PEEP (positive end-expiratory pressure), PIP (peak inspiratory pressure), Pplat (plateau Pressure).

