7.1.4 ICU discharge (Day X – whenever it occurs)

- Arterial Blood Gas (ABG) Analysis
- Ventilatory support: extubation date recorded (as applicable) and following ventilation procedures recorded
- Ventilatory parameters: PaO₂/FiO₂, FiO₂, tidal volume (TV), respiratory rate (RR), static compliance (Cstat), dynamic compliance (Cdyn), PEEP (positive end-expiratory pressure), PIP (peak inspiratory pressure), Plateau Pressure (Pplat)
- Laboratory assessments blood count, bilirubin, creatinine, eGFR, LDH, D-dimer, CRP, procalcitonin
- Vital signs will be obtained as appropriate
- SOFA score is calculated considering PaO₂/FiO₂, Glasgow coma scale, mean arterial pressure, and bilirubin, platelet and creatinine levels
- AEs review (including SAEs)
- Concomitant medications and procedure review as applicable
- Discharge date from ICU

7.1.5 Day 28

It's the last day of follow up. Whenever the patient has been discharged home from ICU a phone call FUP is requested.

The following procedures will be followed if the patient is still hospitalized:

- Arterial Blood Gas (ABG) Analysis

Clinical Study Code No.: CLI-050000-04	Version No.: 4.0
EUDRACT No.: 2020-002632-75 – IND No: 153286	Date: 02 MAR 2021

- Ventilatory support: extubation date recorded (as applicable) and following ventilation procedures recorded
- Ventilatory parameters: PaO₂/FiO₂, FiO₂, tidal volume, respiratory rate, static compliance (C_{stat}), dynamic compliance (C_{dyn}), PEEP (positive end-expiratory pressure), PIP (peak inspiratory pressure), Plateau Pressure
- Laboratory assessments: blood count, bilirubin, creatinine, eGFR, LDH, D-dimer, CRP, procalcitonin
- Vital signs will be obtained as appropriate
- SOFA score is calculated considering PaO₂/FiO₂, Glasgow coma scale, mean arterial pressure, and bilirubin, platelet and creatinine levels
- AEs review (including SAEs)
- Concomitant medications review as applicable

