4.1.2.2 Others Secondary Efficacy Variables

- Number of days alive and ventilator-free **at Day 28**
- Mortality **at Day 21 and Day 28**
- Number of days alive and free from invasive ventilation **at Day 21 and Day 28**

- Number of days alive and free from non-invasive ventilation (NIV) at **Day 21 and Day 28**
- Percentage of subjects with improvement in severity status defined as a decrease in the severity score at **Day 28 or Discharge**, whichever comes first. Severity score will be defined as Mild, Moderate, Severe or Death based on PaO₂/FiO₂ ratio and subject status at Day 28 and numerically rated from 1-4 respectively:

Severity	Variable	Criteria
Mild -1	PaO ₂ /FiO ₂ Ratio	200 mmHg < PaO ₂ /FIO ₂ ≤ 300 mmHg
Moderate - 2	PaO ₂ /FiO ₂ Ratio	100 mmHg < PaO ₂ /FIO ₂ ≤ 200 mmHg
Severe - 3	PaO ₂ /FiO ₂	Ratio PaO ₂ /FIO ₂ ≤ 100 mmHg
Death - 4	Patient Status	Yes/No

- Change from baseline in PaO₂/FiO₂ ratio at **6 and 12 hours following administration of each dose** in the treated group and at the similar timepoints in the control group (6, 12, 30, 36, 54 and 60 hours after randomisation)
- Change from baseline in PaO₂/FiO₂ ratio at additional timepoints (i.e. every 24 hours after treatment/randomisation until the subject is discharged from the ICU)
- Percentage of subjects alive and with PaO₂/FiO₂ improvement of >20% at **6 and 12 hours following administration of each dose** in the treated group and at similar timepoints in the control group (6, 12, 30, 36, 54 and 60 hours after randomisation)
- Percentage of subjects alive and with PaO₂/FiO₂ improvement of >20% at the additional timepoints (i.e. every 24 hours after treatment/randomisation till the subject is discharged from the ICU)
- Change from baseline in FiO₂ at **6 and 12 hours following administration of each dose** in the treated group and at similar timepoints in the control group (6, 12, 30, 36, 54 and 60 hours after randomisation)
- Change from baseline in FiO₂ at additional timepoints (i.e. every 24 hours after treatment/randomisation until the subject is discharged from the ICU)
- Length of ICU stay (days) **at Day 28**. Subjects who die or are mechanically ventilated longer than this period are assigned with 28 days
- Percentage of subjects alive and out of ICU **at Day 28**
- Delta SOFA Score and sub-score component measured on **Day 3 and Day 28 or Discharge** whichever comes first

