9.3.4 Improvement in Severity Status at Day 28 or Discharge

The severity status will be based on the ventilatory parameters form for PaO₂/FiO₂ ratio at baseline and at Day 28 or Discharge (whichever comes first) and on Study Termination form for the death, according to the scale below:

Severity	Variable	Criteria
Mild - 1	PaO ₂ /FiO ₂ Ratio	200 mmHg < PaO ₂ /FIO ₂ ≤ 300 mmHg
Moderate - 2	PaO ₂ /FiO ₂ Ratio	100 mmHg < PaO ₂ /FIO ₂ ≤ 200 mmHg
Severe - 3	PaO ₂ /FiO ₂	Ratio PaO ₂ /FIO ₂ ≤ 100 mmHg
Death - 4	Patient Status	Yes/No

In case of multiple assessments done on same date, the last assessment will be taken into account for the severity status definition.

The severity status, the number and percentage of subjects with an improvement (i.e. a decrease of at least one point of severity) from baseline to Day 28 or Discharge will be summarized. A shift table displaying the severity at baseline and at day 28 or Discharge will also be provided.

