9.3.10 Change from Baseline in SOFA Score

SOFA sub-score and total score actual values and change from baseline will be presented using descriptive statistics at Day 3, ICU discharge or Day 28 (whichever comes first).by treatment group. The change from baseline to Day 3 and to ICU Discharge or Day 28 difference between the two groups for each sub-score and for total score will be described.

A graph displaying the means and SD for each timepoint (until the subject is discharged from ICU) will be also provided for each treatment group.

9.3.11 Percentage of Subjects Alive and Organ Failure Free (SOFA score=0) at Day 28 or Discharge

The subject will be defined alive and organ failure free at Day 28 or Discharge if:

- Date of Death is missing or > MIN (Date of Day 28 or Date of Discharge)

AND

- Total SOFA Score = 0 at Day 28 or at Discharge

The percentage will be summarized.

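### Day 28 SOFA is limited to ICU patients in the schedule but covers any inpatient in Protocol 7.1.5, and SAP 9.3.11 lets a ward patient qualify as organ-failure free on either of two values

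*Protocol*

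**What the plan says.** **Who is measured on Day 28.**
- Protocol 7.1, Day 28 column, rows for arterial blood gas, ventilator parameters, laboratory tests and SOFA: "Once if not discharged from ICU". SAP Table 1 repeats this.
- Protocol Outline, study plan, poractant alfa group: the last evaluation takes place on the ICU "or by phone call if the patient has been discharged from ICU by that time". The control group text has the evaluation on the ICU, or a call if the patient has already been discharged.
- Protocol 7.2.1.1 takes the last blood samples at the earlier of Day 28 and ICU discharge.
- Protocol 7.1.5 differs. "The following procedures will be followed if the patient is still hospitalized" introduces a list that includes blood gases, ventilatory parameters, laboratory tests and SOFA. The call has a narrower trigger: "Whenever the patient has been discharged home from ICU a phone call FUP is requested".

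Protocol 3.2 expects some patients to move from ICU to another department and to remain in the study.

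**Which value counts.**
- Protocol section 8 and SAP 4.1.2.2 define organ-failure freedom (alive, SOFA of 0) at Day 28 or discharge, taking the earlier.
- SAP 9.3.11 applies a MIN of the two dates in its death condition. Its SOFA condition reads "Total SOFA Score = 0 at Day 28 or at Discharge".
- SAP 9.3.10 summarises delta SOFA "at Day 3, ICU discharge or Day 28 (whichever comes first").
- SAP 9.3.4 takes severity "at baseline and at Day 28 or Discharge (whichever comes first"). The definition in SAP 4.1.2.2 also refers to "subject status at Day 28 and numerically rated from 1-4 respectively".

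**The concern.** The two visit rules disagree for one group of patients: those out of ICU but still in hospital on Day 28. Whether such a patient has a Day 28 SOFA depends on which passage the site followed.

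That would do little harm if the analysis always took the earlier value, because the ward value would never be used. The SOFA line of SAP 9.3.11 does not say so. Read literally, it accepts a score of 0 at either time. Ward patients measured under 7.1.5 then have two opportunities to qualify, and patients already home, or on a ward at a site that followed the schedule, have one. The reported percentage would depend partly on site practice and on where patients were on Day 28. SAP section 12, which lists changes from the protocol, records no change to the timing of this endpoint.

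**Working it through.** The plan gives no figure on this point, so the check compares the text first and then gives an illustration.

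**Step 1: one patient through the rules.** Suppose patient A leaves ICU on Day 8 with SOFA above 0, is on a ward on Day 28, and would score 0 that day. Patient B has the same score at ICU discharge but is home by Day 28.

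| Patient | Site follows | SOFA values available | SAP 9.3.11 as written | Earlier-of rule |
|---|---|---|---|---|
| A | Schedule | ICU discharge only | Not a responder | Not a responder |
| A | Section 7.1.5 | ICU discharge and Day 28 | Responder | Not a responder |
| B | Either | ICU discharge only | Not a responder | Not a responder |

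Only the second row changes. It needs both conditions: the site followed 7.1.5, and the SOFA line was programmed literally. The either-or wording can only add responders, because a patient with 0 at ICU discharge qualifies whatever the later score.

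**Step 2: which rule has data for everyone.** SOFA is scheduled at ICU discharge (Day X) and on Day 28 for patients still in ICU. Nothing is scheduled at hospital discharge. The earlier of ICU discharge or Day 28 therefore has a planned measurement for every survivor in follow-up, and it agrees with SAP 9.3.10 and Protocol 7.2.1.1.

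**Step 3: possible size, on assumed inputs only.** Let w be the share of an arm on a ward on Day 28 and measured there, p the probability of SOFA 0 at ICU discharge in those patients, and q the probability of 0 on Day 28 given that it was above 0 at ICU discharge.

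Added responder share = w × (1 − p) × q

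- Low end (w = 0.10, p = 0.30, q = 0.20): 0.10 × 0.70 × 0.20 = 0.014, or 1.4 points.
- High end (w = 0.30, p = 0.10, q = 0.60): 0.30 × 0.90 × 0.60 = 0.162, or 16.2 points.
- Middle case (p = 0.20, q = 0.30): a measured ward patient passes with probability 0.20 + 0.80 × 0.30 = 0.44 instead of 0.20. At w of 0.10 and 0.30 the arm gains 0.24 × 0.10 = 2.4 and 0.24 × 0.30 = 7.2 points.

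These are gains within one arm. With the same w, p and q in both arms, the between-arm effect is 0. In the middle case, ward shares of 10% and 30% would give 7.2 − 2.4 = 4.8 points. No passage gives a ward share for either arm.

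One reclassified patient is 1/28 = 3.6 points in the planned control arm and 1/42 = 2.4 points in the planned poractant alfa arm. SAP section 12 says recruitment closed below 70, so one patient may weigh more.

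**The case against.** The strongest reply is that context settles most of this. ICU discharge is the only discharge visit in either document: it is the Day X column of the schedule, section 7.1.4, and the last visit named in SAP 13.2.1. The organ-failure endpoint carries the earlier-of rule in the protocol and in SAP 4.1.2.2, the companion condition in 9.3.11 uses MIN, and the notes to Table 14.2.14 call for a single timepoint. On this view the SOFA line is a shortened sentence that a careful programmer would read correctly. The endpoint is secondary, not key, and SAP 7.5 and section 12 leave it to description without a model or test.

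Much of that stands, and it limits the point. It does not remove it: 9.3.11 is the derivation a programmer works from, its wording departs from the definition, and 7.1.5 creates the second value that makes the departure matter.

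A reader might infer more than the documents support:
- **That severity status is equally affected.** SAP 9.3.4 already takes the earlier time. A different value needs Discharge to mean hospital discharge, for which no measurement is scheduled.
- **That delta SOFA is affected.** SAP 9.3.10 names ICU discharge and takes the earlier time, so a ward patient's value is fixed.
- **That the treatment comparison is biased by a known amount.** The percentages above rest on assumed rates, and nothing indicates that ward shares differ between arms.

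**Conclusion.** Two defects are established from the text. The Day 28 measurement rule in 7.1.5 contradicts the schedule, the outline and 7.2.1.1 for patients on a ward. The SOFA condition in SAP 9.3.11 omits the earlier-of rule that defines its endpoint, so a ward patient measured at both times can qualify on the later value.

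The effect is confined to one responder endpoint, organ-failure freedom. Its size cannot be derived from the documents; the 1.4 to 16.2 points within an arm hold only under the assumed ranges of w, p and q. The severity endpoint needs its term made explicit, but no error in its value is shown. The primary endpoint and the sample size are untouched. The correction is worth making because it costs only wording and the percentage will be reported by arm.

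**What to change.** - In SAP 9.3.11, make the second condition a total SOFA score of 0 at the earlier of ICU discharge or Day 28. SAP 9.3.8 allows for readmission to ICU, so also say which ICU discharge counts.
- For the SOFA and PaO2/FiO2 measurements, write ICU discharge in place of Discharge alone in SAP 4.1.2.2, 9.3.4 and 9.3.11, and in the matching protocol text (outline, section 8, section 12.3.5). This follows SAP 9.3.10 and Protocol 7.2.1.1.
- Keep Day 28 vital status in the severity definition. Removing the Day 28 reference altogether could let a patient who improved, left ICU and then died before Day 28 count as improved. That would conflict with SAP 7.2, which treats death as failure for binary endpoints. Only the timing of the PaO2/FiO2 value needs the ICU-discharge wording.
- Reconcile Protocol 7.1.5 with the schedule. As recruitment has closed, this can no longer change collection, so document which Day 28 ward values were obtained.
- List any Day 28 ward values without using them for these endpoints.

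The cost is wording in the SAP and the matching protocol passages, with no new data. The downside is that Day 28 ward values are listed only.

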7.1.1 Screening and eligibility assessment

Screening evaluations must be completed and reviewed to confirm that potential participants meet eligibility criteria. The investigator will maintain a screening log to record details of all participants screened and to confirm eligibility or record reasons for screening failure, as applicable.

Clinical Study Code No.: CLI-050000-04	Version No.: 4.0
EUDRACT No.: 2020-002632-75 – IND No: 153286	Date: 02 MAR 2021

Procedures conducted as part of the participant's routine clinical management (e.g. blood count) and obtained before informed consent may be used for screening or baseline purposes provided the procedures meet the protocol-specified criteria.

All screening procedures have to be completed/performed before the randomization.

After verification of any inclusion/exclusion criteria, those intubated patients with ARDS due to COVID-19 will be included in the study.

Date of patient intubation and mechanical ventilation start time is recorded for both the groups.

The following assessment will be collected:

- Informed consent for participation in the study (*refer to [section 15](#) for detailed informed consent procedure*)
- Demographics
- Medical history (includes past and current relevant medical conditions)
- Full physical examination including height and weight
- Arterial Blood Gas (ABG) Analysis
- Ventilatory support
- Ventilatory parameters: PaO₂/FiO₂, FiO₂, tidal volume (TV), respiratory rate (RR), static compliance (Cstat), dynamic compliance (Cdyn), PEEP (positive end-expiratory pressure), PIP (peak inspiratory pressure), Plateau Pressure (Pplat).
- Laboratory assessments: blood count, bilirubin, creatinine, eGFR, LDH, D-dimer, CRP, procalcitonin and urine beta HCG (*only for eligibility criteria*). SARS-Cov-19 rtPCR (*as available, at least before randomization*)
- Vital signs will be obtained as appropriate
- SOFA score is calculated considering PaO₂/FiO₂, Glasgow coma scale, mean arterial pressure, and bilirubin, platelet and creatinine levels
- Thoracic CT scan or Chest XR already available as part of the standard care
- AEs review (including SAEs)
- Concomitant medications and procedure review

7.1.2 Day 1, Day 2 and Day 3 for treated group [up to 72 hours for control group]

On Day 1, within 48 hr after intubation, the patients will be randomised in the poractant alfa treated group or in the control one with the 3:2 ratio.

In case the patient will be assigned to the poractant alfa treated group, the treatment must start soon after the randomization (max 2 hr), and within 48hr after intubation

The following procedures for treated group or for control group will be conducted according to the frequencies reported in the above flowchart:

- Treatment procedure for poractant alfa as described in detail in [section 6.2](#). One administration per day with a 24 hours interval
- Arterial Blood Gas (ABG) Analysis
- Ventilatory support
- Ventilatory parameters: PaO₂/FiO₂, FiO₂, tidal volume (TV), respiratory rate (RR), static compliance (Cstat), dynamic compliance (Cdyn), PEEP (positive end-expiratory pressure), PIP (peak inspiratory pressure), Plateau Pressure (Pplat)
- Laboratory assessments for mechanistic analysis: blood sampling and bronchial washings; bronchoscopic washings performed as clinically indicated only, with surplus samples retrieved for mechanistic study as available (for more details ref. to [section 7.2](#))

Clinical Study Code No.: CLI-050000-04	Version No.: 4.0
EUDRACT No.: 2020-002632-75 – IND No: 153286	Date: 02 MAR 2021

- Laboratory assessments: blood count, bilirubin, creatinine, eGFR, LDH, D-dimer, CRP, procalcitonin
- Vital signs will be obtained as appropriate
- SOFA score is calculated considering PaO₂/FiO₂, Glasgow coma scale, mean arterial pressure, and bilirubin, platelet and creatinine levels
- AEs review (including SAEs)
- Concomitant medications and procedure review as applicable

7.1.3 Day 4 – 27 recording:

The following procedures for treated group or for control group will be conducted according to the above flowchart

- Arterial Blood Gas (ABG) Analysis
- Ventilatory support: extubation date recorded (as applicable) and following ventilation procedures recorded
- Ventilatory parameters: PaO₂/FiO₂, FiO₂, tidal volume (TV), respiratory rate (RR), static compliance (Cstat), dynamic compliance (Cdyn), PEEP (positive end-expiratory pressure), PIP (peak inspiratory pressure), Plateau Pressure (Pplat)
- Vital signs will be obtained as appropriate
- AEs review (including SAEs)
- Concomitant medications and procedure review as applicable
- Discharge date from ICU if applicable
- Laboratory assessments for mechanistic analysis (only at 96h): bronchial washings, and blood samples, bronchoscopic washings performed as clinically indicated only, with surplus samples retrieved for mechanistic study as available (for more details ref. to [section 7.2](#)). They are planned only for patients recruited in UK

7.1.4 ICU discharge (Day X – whenever it occurs)

- Arterial Blood Gas (ABG) Analysis
- Ventilatory support: extubation date recorded (as applicable) and following ventilation procedures recorded
- Ventilatory parameters: PaO₂/FiO₂, FiO₂, tidal volume (TV), respiratory rate (RR), static compliance (Cstat), dynamic compliance (Cdyn), PEEP (positive end-expiratory pressure), PIP (peak inspiratory pressure), Plateau Pressure (Pplat)
- Laboratory assessments blood count, bilirubin, creatinine, eGFR, LDH, D-dimer, CRP, procalcitonin
- Vital signs will be obtained as appropriate
- SOFA score is calculated considering PaO₂/FiO₂, Glasgow coma scale, mean arterial pressure, and bilirubin, platelet and creatinine levels
- AEs review (including SAEs)
- Concomitant medications and procedure review as applicable
- Discharge date from ICU

7.1.5 Day 28

It's the last day of follow up. Whenever the patient has been discharged home from ICU a phone call FUP is requested.

The following procedures will be followed if the patient is still hospitalized:

- Arterial Blood Gas (ABG) Analysis

Clinical Study Code No.: CLI-050000-04	Version No.: 4.0
EUDRACT No.: 2020-002632-75 – IND No: 153286	Date: 02 MAR 2021

- Ventilatory support: extubation date recorded (as applicable) and following ventilation procedures recorded
- Ventilatory parameters: PaO₂/FiO₂, FiO₂, tidal volume, respiratory rate, static compliance (C_{stat}), dynamic compliance (C_{dyn}), PEEP (positive end-expiratory pressure), PIP (peak inspiratory pressure), Plateau Pressure
- Laboratory assessments: blood count, bilirubin, creatinine, eGFR, LDH, D-dimer, CRP, procalcitonin
- Vital signs will be obtained as appropriate
- SOFA score is calculated considering PaO₂/FiO₂, Glasgow coma scale, mean arterial pressure, and bilirubin, platelet and creatinine levels
- AEs review (including SAEs)
- Concomitant medications review as applicable

